### Self-completed Ecological Daily Assessments (<3 minutes each day)

Using the Lumen companion application participants complete ecological end-of-day assessments of mood, stress, appraisal, and coping for 7 days every 2 weeks (over 16 weeks).

**Intervention Orientation.** Participants in the intervention arm attend a Lumen orientation visit (60 minutes) during which they will be given a Lumen intervention tutorial and receive a study iPad, configured to limit access to only the Lumen intervention enabled on the device. Before leaving participants are scheduled for the first PST session with Coach Lumen. As needed, Lumen intervention orientations can be done remotely.

**Intervention data collection.** Secure study iPads used by participants in the intervention arm are enabled with Lumen PST. Participants complete 8 PST sessions beginning with 4 weekly and then 4 biweekly intervals over 12 weeks on their assigned iPad. At the end of each PST session, participants are prompted to schedule their next session with Coach Lumen. They receive automated reminder notifications 1 day prior to their next session and on the session day and have the opportunity to make up missed sessions. Intervention participants also complete the PHQ9 and GAD7 and user experience surveys at all PST sessions. Upon completion of the intervention participants will receive a certificate of completion signed by [name]. They may also complete a post-intervention interview via Zoom to characterize participant perspectives regarding their Lumen use experience.

**Intervention fidelity assurance.** All PST sessions that participants complete with Lumen are audiorecorded. Session recordings and transcripts are stored on the Amazon Web Services (AWS) in study configured accounts, with coded identifiers (see Section 7.). These materials will be used to evaluate treatment fidelity and user-Lumen interaction.

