In addition, the conversation manager also manages the “state” of the conversation—including the flow of interactive conversation (e.g., the flow of the above-mentioned steps), and adaptive responses based on user input. The conversational state is adaptively managed based on user input. Towards this end, user “intents” or statements are parsed and mapped into pre-defined categories, which are then mapped to the appropriate state in the PST interaction to deliver relevant content, aligned with the user input. The conversation manager also provides dynamic support for functions such as resume, which allows participants to re-start a previously incomplete PST session. Such stop-restart functions provide flexibility in conversational interactions, affording perceptions of realistic conversational interactions.

The conversation manager also interacts with a **context manager** module that provides situated and contextual information regarding Lumen sessions. The context manager primarily controls three aspects: persistence of therapy content across sessions, scheduling/re-scheduling of sessions, and integrating external content (e.g., surveys, EMAs) into the Lumen sessions. The context manager dynamically tracks user problems (see step 1 above), and potential action plans that were previously developed and evaluates adherence to those plans in ensuing sessions. Such dynamic follow-up increases the persistence and continuity of therapy across sessions, developing trust and confidence in the virtual coach. Similarly, the context manager tracks session progress (e.g., session 5), and helps participants schedule and re-schedule sessions. With its integration with an external scheduling database (in REDCap), follow-up emails and messages are tracked to ensure that the therapy sessions are synchronized with participant needs. Finally, the context manager also interacts with the REDCap database to incorporate survey responses (e.g., completion of the PHQ-9 and GAD-7 surveys) into the Lumen session. For example, prior to the start of each Lumen session, participants are asked to complete the PHQ-9 and GAD-7 surveys; if incomplete (or partially complete), Coach Lumen reminds the user to complete the survey prior to re-starting the session. Further, if a user delays session attendance after having completed the surveys, Lumen checks whether a survey is current (within 3 days) to

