Longitudinal mixed modeling will be applied to analyses of the ecological measures (mood, stress, appraisal, and coping) where the design is  $\text{Group} \times \text{Time} = 2 \times 8$  as these measures will be obtained (using a validated measurement burst design) daily for 7 days every 2 weeks (on weeks 0, 2, 4, 6, 8, 10, 12, 16). During active treatment in the Lumen group, this will occur for 3 days prior to, the day of, and 3 days after each scheduled PST session. For waitlist controls, this will occur for 7 days starting on Sunday of each assigned week. This allows us rich and detailed information on ambulatory changes over the course of treatment, as well as estimates of proximal responses to treatment within 3 days immediately post a PST session. For example, using the means of ecological measures over the 3 pre-PST days (to avoid confounding estimates with proximal treatment response) in the Lumen group and the first 3 days in the waitlist control group every 2 weeks as DVs, we will characterize their trajectory of change in terms of orthogonal linear, quadratic, and cubic components. We also will examine regression spline versions of these trajectories for visualization and interpretation. In a more exploratory vein, for each set of 7 daily ecological measures, collected biweekly, we will use piecewise linear models to characterize proximal responses to treatment based on the change of the 3 post-treatment days' means from the 3 pre-treatment days' means (omitting treatment day 4) in the Lumen group and the corresponding biweekly change of the last 3 days' means from the first 3 days' means (omitting day 4) in the waitlist control group. As these differences are nested within the 8 biweekly measurement bursts, and thus can be examined longitudinally, we can consider whether there is change over weeks in patients' proximal responses to each PST session (in terms of the ecological measures). In all analyses, all available data for each DV will be used and missing data will be handled directly through maximum-likelihood estimation via mixed modeling, supplemented with imputation and sensitivity analysis (see Handling Missing Data in Section B.4 below).

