**Ecological end-of-day assessments:** Ecological measures of mood, stress, appraisal, and coping will be available at weeks 0, 2, 4, 6, 8, 10, 12 and 16 (for a total of 8 occasions). Each week's assessment is based on 7 contiguous days' end-of-day assessments of the 4 ecological measures, with day 4 being the day of PST treatment in the Lumen group. Thus, the mean of the 3 pre-treatment days on these variables provides an indication of a participants' status immediately prior to each PST session; the mean of the 3 post-treatment days on the same variables provides an indication of a participants' status immediately post the session. For this secondary dosing analysis, we can mirror the dosing analysis by regressing change in the 7-day mean from week 0 to week 16 for each of the 4 ecological measures on the 4 dose variants. Importantly, there are 6 intermediate measurement occasions in addition to week 16, so we will be able to examine trajectories of change from week 0 to week 2, to week 4, and so on, to week 16. Moreover, for each ecological measure a set of time-related variables may be constructed, such as overall 7 days' means, 3 pre-treatment days' means, and differences between 3 pre-treatment days' means and 3 post-treatment days' means (omitting treatment day 4), so we will be able to examine trajectories of change in these variables. It is also important to note that the 4 dosing variables in these longitudinal regression models reflect the dose received up to that point in the treatment. This provides a view of how accurately the dosing variables perform for the ecological measures over the entire span of the treatment. These analyses will use time-varying mixed models where the DV (e.g., mood) and the dose measure vary over the 16-week period. The models for each dose measure (e.g., number of sessions) will include separate polynomial terms for linear, quadratic, and cubic rates of change in the DV over time. Alternatively, we will model the log of the dose measure (e.g., number of sessions) considering that some studies of in-person psychotherapy reported a negatively accelerated relationship between dose and treatment progress, suggesting a pattern of successively diminishing returns with increasing dose. We will compare model fit for the polynomial and logarithmic models using Schwartz Bayesian Information Criterion (BIC).

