**Treatment progress measures:** To monitor treatment progress, symptoms (PHQ9, GAD7) and treatment acceptability (usability, user experience, and treatment alliance) will be measured in each PST session at weeks 1, 2, 3, 4, 6, 8, 10, and 12 (for a total of 8 occasions). Similar to the analyses of ecological measures as described above, we will implement polynomial and logarithmic models and compare model

fit using BIC. These regressions'  $R^2$ 's will allow us to examine in detail the relationship of treatment progress and cumulative dose, with fidelity-to-PST taken into account using the fidelity-weighted number and length of PST sessions. Additionally, as is common in psychotherapy in general, it is possible that not all participants will complete the full 8 sessions as some may drop out early owing to either lack of improvement or “enough” improvement based on self-assessment or yet other reasons related or unrelated to the treatment. Using the Good-Enough-Level (GEL) model, some studies of in-person psychotherapy showed that the rate of change varied as a function of treatment duration, namely, the rate of change (progress) was faster for patients attending fewer sessions but slower for those attending more sessions. In other words, patients may remain in treatment until they improve. To explore whether a similar pattern is present for Lumen PST, we will apply the GEL modeling approach by extending the polynomial models for treatment progress measures, in particular, PHQ9 and GAD7, to include a fixed effect of total treatment dose (e.g., total number of sessions) and interactions between total treatment dose and linear, quadratic, and cubic rates of change. Essentially, the GEL model is a stratified analysis that examines dose effects across strata of participants with similar treatment dose (e.g., similar number of sessions attended), as opposed to aggregate dose effects across all participants. Furthermore, we will conduct exploratory analyses of baseline characteristics in relation to the dose effects on neural targets, PROs, ecological measures, and treatment progress measures. We anticipate that baseline characteristics (e.g., severity at presentation, sex as a biological variable, sociodemographics) may be related to dosing estimates (e.g., via actual sessions completed). To explore these relationships, baseline characteristics and their interactions with dose measures will be added to the models as described above.

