## Appendix 4. Study Event Windows

### Event windows (in Days)

Preferred windows (in Days)	ES	V1	EMA#1	R														V2		
Lumen PST:					Orient.	S1	S2	S3	S4		S5		S6		S7		S8			
Week (indexed from randomization) #: from	-4	-2		0	1	1	2	3	4		6		8		10		12		14	
to	-2	-1			2	3	4	5	6		8		10		12		14		18	
IES-eligible to eConsent, max. days	14			Randomization																
eConsent to V1, max. days		14																		
IES-eligible to V1 (rescreen if IES-V1>90d), max. days		28																		
V1 to EMA#1 start (automated), max. days		1																		
V1 to Randomization, max. days			10																	
Randomization to Lumen Orientation Visit, max. days						14														
Lumen Orientation to Session 1, max. days							7													
Lumen Session to Session, max. days								7	7	7		14		14		14		14		
Randomization to V2, target 112d (16 weeks) +/- allowable 14d window (14-18 weeks)																				112 +/-14

Abbreviations: IES, initial eligibility screening; EMA, ecological daily assessment; PST, problem solving treatment; S1-S8, sessions 1-8 with Lumen; V1, visit 1; V2, visit 2

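### Diary days are labelled pre and post from the scheduled session, so a session that slips after the burst has begun misclassifies them; arm timing on nominal weeks can also differ by up to about two weeks

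*Combined protocol and SAP*

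**What the plan says.** Appendix 3, B.2 sets the collection rule for the Lumen arm during active treatment: "this will occur for 3 days prior to, the day of, and 3 days after each scheduled PST session". Footnote c of Appendix 2 repeats it. B.2 then contrasts the mean of the last three days with the mean of the first three, leaving out the fourth, as the proximal response to a session. B.3.c describes the same burst "with day 4 being the day of PST treatment in the Lumen group" and says pre and post variables may be built from it.

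The documents expect session dates to move. Section 6.0 says participants "have the opportunity to make up missed sessions". Appendix 1, Section A provides for what happens "if a user delays session attendance after having completed the surveys": Lumen checks that the PHQ-9 and GAD-7 are no more than 3 days old. Appendix 1, Section B lets appointments be adjusted and carries the change into REDCap, which, per Table 1 of that appendix, also delivers the diaries.

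On timing, B.2 describes the between-arm model as Group by Time, 2 x 8, on weeks 0, 2, 4, 6, 8, 10, 12 and 16. The Lumen calendar is built from the date of the first session (Appendix 1, Section B). For the other arm: "For waitlist controls, this will occur for 7 days starting on Sunday of each assigned week". Assigned week is not defined further. Appendix 4 gives session windows in weeks from randomization.

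**The concern.** The diary is collected around a planned date but analysed as though the plan was kept. If the session slips while the burst stays in place, days before the session, or the session day itself, are averaged into the post-treatment mean, and the proximal response shrinks toward zero. The slippage need not be random: B.4 itself says participants may miss sessions because they have improved or because they are discouraged. The missing-data tools in B.4 do not help, because these days are observed and merely carry the wrong label.

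The second issue is elapsed time. A Lumen burst follows its session and a waitlist burst follows a calendar week. If both are entered under the same nominal week, any common trend over time can appear as an arm difference.

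At stake are the session-response estimates that B.2 presents as a gain from the burst design, and the diary trajectories by arm.

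**Working it through.** **Which bursts contain a session.** B.3.c has progress "measured in each PST session at weeks 1, 2, 3, 4, 6, 8, 10, and 12". Bursts fall in weeks 0, 2, 4, 6, 8, 10, 12 and 16. The overlap is weeks 2, 4, 6, 8, 10 and 12, so the day-4 label has meaning in 6 of the 8 bursts (S2, S4, S5, S6, S7 and S8).

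**Day labels.** Let the session slip by k days while the burst stays put. The session then falls on burst day 4 + k. Classify days 5 to 7 against it. For the share of the post-minus-pre contrast that is kept, assume a step response (the documents give no response shape) and show two onsets: (a) the effect starts the next day, share = max(0, 3 - k)/3; (b) the session-day end-of-day diary already reflects it, share = min(1, max(0, 4 - k)/3).

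| Slip k | Session on day | Days 5-7 before session | On session day | After session | Kept (a) | Kept (b) |
|---|---|---|---|---|---|---|
| 0 | 4 | 0 | 0 | 3 | 1 | 1 |
| 1 | 5 | 0 | 1 | 2 | 2/3 | 1 |
| 2 | 6 | 1 | 1 | 1 | 1/3 | 2/3 |
| 3 | 7 | 2 | 1 | 0 | 0 | 1/3 |
| 4 or more | 8 or later | 3 | 0 | 0 | 0 | 0 |

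A missed session behaves like the last row. Days 1 to 3 precede a late session in every row, so the three-day pre-session means that B.2 offers for the trajectory are not mislabelled by lateness. The error sits in the post mean and in the contrast.

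**Session windows, reproduced first.** Appendix 4 maxima are 14 days for "Randomization to Lumen Orientation Visit, max. days", 7 days from orientation to S1, then gaps of 7, 7, 7, 14, 14, 14 and 14 days.

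- Latest S1 = 14 + 7 = day 21. Adding the gaps gives days 28, 35, 42, 56, 70, 84 and 98 for S2 to S8. S1 to S8 are then weeks 3, 4, 5, 6, 8, 10, 12 and 14, which matches the printed upper limits.
- Earliest S1 = day 7. The same gaps give days 14, 21, 28, 42, 56, 70 and 84, so S1 to S8 are weeks 1, 2, 3, 4, 6, 8, 10 and 12, which matches the printed lower limits.
- Every session has a 14-day spread. S2, nominally week 2, may fall from day 14 to day 28; S8, nominally week 12, from day 84 to day 98.

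Appendix 1, Section A counts the minimum gaps (6 or 13 days) from the last completed session, so a late start is largely carried forward.

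**Arm offset.** Assumption: waitlist assigned weeks are counted from randomization. Take week 2. The Lumen burst starts 3 days before S2, on day 14 - 3 = 11 to day 28 - 3 = 25.

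- If the waitlist Sunday falls on or after day 14 (days 14 to 20), Lumen minus waitlist runs from 11 - 20 = -9 to 25 - 14 = +11 days.
- If it falls on or before day 14 (days 8 to 14), the range is 11 - 14 = -3 to 25 - 8 = +17 days.

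The other session weeks give the same ranges. At the far end, a latest S8 burst covers days 95 to 101, while Visit 2 may take place from day 112 - 14 = 98.

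**What an offset could do.** Illustration only, with an assumed common trend of 0.02 to 0.10 SD per week and no treatment effect: a 2-week offset gives an apparent arm difference of 2 x 0.02 = 0.04 to 2 x 0.10 = 0.20 SD.

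**The case against.** A diary must be triggered in advance, so the scheduled date is the natural anchor for collection. REDCap holds both the calendar and the diary delivery, so a session rescheduled ahead of time may well take its burst with it. That stands. It would be wrong to infer that every rescheduling leaves the burst behind; what remains is a session delayed or missed after the burst has opened, 3 days before the scheduled date.

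A reader might also take the 3-day currency check as the protocol's tolerance for late sessions. It governs only how recent the PHQ-9 and GAD-7 must be, and says nothing about how late sessions are expected to run. Nor does any slip at all turn post days into pre-session days: at 1 day, day 5 is the session day and days 6 and 7 still follow it.

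On arm timing, the 2 x 8 notation may describe measurement occasions rather than how time is coded, and the waitlist week is undefined. A firm 2-week mismatch therefore cannot be read from the documents. Nor should the latest S2 on day 28 be read as a 4-week gap from the first burst: that burst starts within a day of Visit 1, which may precede randomization by up to 10 days. Still, no time variable other than the nominal week is named, and Appendix 4 does allow the spread.

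Finally, B.3.c is a Lumen-only analysis. Its week 0 to 16 regression uses 7-day means from bursts without a session, and its longitudinal models use dose received to date, so the day label does not enter the former and touches the latter only where pre and post variables are built. The between-arm contrast belongs to B.2, where the proximal analysis is called exploratory.

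**Conclusion.** The point holds in limited form. Under the stated rule, observed diary days are misclassified whenever a session slips or is missed after its burst has opened. The session day enters the post mean at 1 day, pre-session days enter from 2 days, and none of the three days is truly post from 3 days. The contrast is fully lost at 3 or 4 days, depending on the assumed onset. The documents give no share of late sessions, so the overall bias cannot be stated.

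The arm-timing part is an upper bound: sessions up to 14 days after the nominal week, and burst starts differing by -9 to +11 or -3 to +17 days according to how the Sunday is chosen, if waitlist weeks run from randomization. Appendix 4 calls its windows preferred, so real offsets could be larger.

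A reader might infer that the transition decision is at risk. It is not: Criteria 1 and 2 use fMRI and self-report at weeks 0 and 16 and no diary-day labels, and the feasibility and acceptability targets do not use them either. The effect is confined to secondary and exploratory diary analyses.

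**What to change.** - In B.2, and in B.3.c where pre and post variables are built, classify each diary day as pre, session or post from the date of the completed session.
- Use the actual days since randomization of each burst as the time variable, in both arms.
- Define the waitlist assigned week, including its origin and which Sunday is meant.
- Keep every burst in the between-arm comparison. A burst without a completed session has no true post day, so state how it enters. Dropping such bursts would remove data from Lumen only, on adherence after randomization, and would conflict with the commitment in B.2 to use all available data. Restrict to bursts with a completed session only within Lumen or as a sensitivity analysis.
- Report the number of late and missed sessions.

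The cost is SAP wording and modest programming; session interactions and diaries are already stored in AWS and REDCap, so no new data are needed. The downside is unequal numbers of pre and post days per burst, which the model must accommodate.

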#### **B.4. Intention to Treat (ITT) and Handling Missing Data**

Clinical trials such as the one proposed must face the issues of dropout and missing data. We have put in place a strong plan to ensure maximum retention of participants through the course of the study, with a projected 85% or greater retention (see the *Recruitment and Retention Plan*). Data missing completely at random (MCAR) may be analyzed “as is” without imputation, as it does not introduce bias into estimates and inferences. More commonly, data are missing at random (MAR) owing to covariate-dependent events (e.g., irregular work shifts, children’s illness, transportation, and scheduling foul-ups). Our primary analysis technique, linear mixed models, is robust for MAR and provides unbiased estimates of model parameters without imputation. (One may impute as well, but the benefit is usually modestly improved power rather than changes to conclusions.) The more serious concern for behavioral interventions is the possibility that data will be missing not at random (MNAR). This occurs when dropout or missingness is related to the level of the outcome of interest (e.g., a participant’s level of depression or anxiety). If treatment is working well and symptoms of depression and anxiety have lessened, then participants may feel continuation in treatment is not necessary or beneficial. They drop out or miss sessions because the treatment seems to have worked. On the other hand, if participants experience no improvement in symptoms, they may drop out or miss sessions because they are discouraged that the treatment seems not to have worked. In either case, the loss of data is related to the outcomes under study and has the potential to bias the study’s conclusion about the intervention. Handling the problem of MNAR is difficult. First, there is no test for the presence of MNAR (*vs.* MAR). Second, there are many possible underlying sources of MNAR and there is no guarantee that explorations of missing data patterns will clearly reveal those sources. Third, missing data imputation for MNAR necessarily makes strong and untestable statistical assumptions, so that conclusions from imputed MNAR datasets must remain tentative. This picture reinforces our strong commitment to participant retention (see the Study 1 *Recruitment and Retention Plan*).

Missing data imputation implemented via SAS procedures MI, MIANALYZE, and MCMC will be carried out to reexamine all primary and secondary analysis. This effectively implements ITT as traditionally conducted. Specifically, both missing outcomes and covariates will be imputed under the

assumption that data are MAR. The fully conditional specification (FCS) approach allows each variable type to be imputed with an appropriate model: linear, discriminant, logistic, or Poisson regression. The algorithm for FCS is implemented in procedure MI: 100 imputed data sets will be created, each imputation is analyzed using MIXED, and finally MIANALYZE combines 100 sets into final estimates. This approach to MAR has been widely adopted given its robust performance. Because linear mixed models estimated via direct likelihood as in MIXED offer unbiased estimates under MAR, the benefit of multiple imputation lies in compliance with the ITT fill-in requirement and modestly increased power. We anticipate these results to differ little from those provided by the primary analysis.

